#### **10.4.3 Handling of missing values/censoring/discontinuations**

If a patient has not had a PFS event at the time of analysis, he/she will be censored following the rules defined in RECIST v1.1 (please refer to [Appendix 1](#)).

#### **10.4.4 Supportive analyses**

The PPS will be used in a supportive analysis of the primary endpoint.

Additional [REDACTED] supportive analyses will be conducted if appropriate and defined in the RAP.

### **10.5 Secondary objectives**

#### **10.5.1 Key secondary objective(s)**

Not Applicable.

#### **10.5.2 Other secondary efficacy objectives**

Efficacy endpoints ORR, BOR and TTP will be also assessed. irPFS will be derived using irRC ([Appendix 2](#)) based on central assessments. An immune related progression disease (irPD) is confirmed by 2 repeated scans at least 4 weeks apart from date of first documented irPD, and the date of 1st scan is defined as the date of irPD.

Individual lesion measurements, overall lesion response, duration of response (DOR), BOR, irPFS and OS will be listed by patient. BOR and ORR will be summarized by treatment arm with accompanying 95% confidence intervals. OS and DOR will be presented descriptively using Kaplan Meier plots. Median OS and DOR will be estimated along with 95% confidence

intervals. The OS rates along with 95% CIs will be provided at 6, 12, 18 and 24 months for each treatment arm using the Kaplan Meier distribution. A stratified Cox regression model will be used to estimate the HR of PDR001 arm vs. the control arm in OS and irPFS, respectively, along with 95% CI for HR.

### **10.5.3 Safety objectives**

#### **10.5.3.1 Analysis set and grouping for the analyses**

For all safety analyses, the safety set will be used. All listings and tables will be presented by treatment group.

The overall observation period will be divided into three mutually exclusive segments:

1. pre-treatment period: from day of patient's informed consent to the day before first dose of study medication
2. on-treatment period: from day of first dose of study medication to 30 days after last dose of study treatment
3. post-treatment period: starting at day 31 after last dose of study treatment.

Safety summaries will primarily be based on all data from the on-treatment period. Following last administration of study treatment, adverse events (including serious adverse events), and new antineoplastic therapies are collected for a period of 150 days for PDR001 treatment and for a period of 30 days for chemotherapy. Following start of new antineoplastic therapy, only study treatment related adverse events will be collected. Select summaries of related adverse events will be produced for the combined on-treatment and post-treatment periods ([Section 10.5.3.2](#)).

#### **10.5.3.2 Adverse events (AEs)**

Summary tables for adverse events (AEs) have to include only AEs that started or worsened during the on-treatment period, the **treatment-emergent** AEs. However, all safety data (including those from the pre and post-treatment periods) will be listed and those collected during the pre-treatment and post-treatment period are to be flagged.

The incidence of treatment-emergent adverse events (new or worsening from screening/baseline) will be summarized by system organ class and or preferred term, severity (based on CTCAE grades), type of adverse event, relation to study treatment by treatment group.

Deaths reportable as SAEs, and non-fatal serious adverse events will be listed by patient and tabulated by type of adverse event and treatment group.

The following summaries will be produced for the combined on-treatment and post-treatment periods: AEs related to the study treatment by preferred term; SAEs related to the study treatment by preferred term; AEs of special interest related to the study treatment.

#### **10.5.3.3 Laboratory abnormalities**

For laboratory tests covered by CTCAE version 4.03, the study's biostatistical and reporting team will grade laboratory data accordingly. For laboratory tests covered by CTCAE, a Grade 0 will be assigned for all non-missing values not graded as 1 or higher. Grade 5 will not be used.

For laboratory tests where Grades are not defined by CTCAE, results will be graded by the low/normal/high classifications based on laboratory normal ranges.

If the lower limits of normal ranges used in CTCAE definitions are missing, then they have to be replaced by a clinical meaningful limit.

The following summaries will be generated separately for hematology, biochemistry and urinary laboratory tests:

- Frequency table for newly occurring on-treatment Grades 3 or 4.
- Shift tables using CTCAE Grades to compare screening/baseline to the worst on-treatment value.
- For laboratory tests where CTCAE Grades are not defined, shift tables using the low/normal/high/ (low and high) classification to compare screening/baseline to the worst on-treatment value.

Listing of all laboratory data with values flagged to show the corresponding CTCAE Grades and the classifications relative to the laboratory normal ranges.

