### 7.2.2.5 Laboratory evaluations

All laboratory parameters assessed for safety purposes will be evaluated locally (except Cytokines, Serology and EBV test examinations that will be evaluated centrally). Refer to [Table 7-6](#) for a summary of the parameters to be evaluated.

More frequent evaluations may be performed at the investigator's discretion if medically indicated; results should be recorded as unscheduled laboratory assessments.

Novartis will be provided with a copy of the laboratory certification and tabulation of the normal ranges for each parameter required. In addition, if at any time a patient has laboratory parameters obtained from a different outside laboratory, Novartis must be provided with a copy of the certification and a tabulation of the normal ranges for that laboratory.

All females of childbearing potential will have a serum pregnancy test at screening/baseline and/or within  $\leq 72$  hours before first dose of study treatment, day 1 of each cycle and at EOT visit. A urine or serum pregnancy test should be performed every month during and at the end of the safety follow-up period. If the patient is not coming to the clinic for the safety follow-up visits, a urine or serum pregnancy test will be performed at home or at a local doctor's office monthly and the results will be communicated to the site staff. The result will be recorded only in the source documentation, not in the CRF. A positive pregnancy test requires immediate discontinuation of study treatment. In addition, refer [Section 8.3](#) for follow-up and reporting Pregnancies.

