2.8.2 Laboratory data

Laboratory data will be converted into SI units and classified (by Novartis statistical programming) into CTC grades according to CTCAE. Grade 5 will not be used.

A Grade 0 CTC grade will be set when laboratory value is:

- Within LLN and ULN and grading in both direction,
- Below ULN and grading in hyper direction,
- Above LLN and grading in hypo direction.

Laboratory data for which a CTC grading does not exist will be classified into low, normal, or high based on local laboratory normal ranges as applicable. For the laboratory parameters where the CTC grades depend on the normal ranges, when normal ranges are captured as 0 and 888888.xxx or above then the normal ranges and normal ranges indicator should not be present and the corresponding CTC grade should not be derived.

The following summaries will be produced for hematology and biochemistry parameters:

- For parameters with CTC grades: Shifts from baseline to the worst post-baseline CTC grade,
- For parameters with no CTC grades defined: Shifts from baseline to the worst post-baseline using low/normal/high classifications,

The following listings will be produced:

- Listing of patients with laboratory abnormalities of CTC grade 3 and 4

Table 2-4 and Table 2-5 list all laboratory parameters with CTCAE or normal ranges that have been collected in the study. The laboratory parameters that will be summarized in the CSR will be mentioned in the TLF shells document. Other laboratory parameters without confirmed normal ranges include:

EBV test, DNA levels in plasma: ‘Copies/mL’ will be reported units. EBV conversion factor: Copies/mL = $10^{\log \text{IU/mL} / 0.369}$.

Serology exam of Anti-DNA antibodies (Abs), Anti-nuclear abs, Anti-phospholipid abs, Anti-mitochondrial abs.

Table 2-4 Laboratory parameters for which CTCAE grades are defined

Hematology and coagulation		Biochemistry	
White Blood Cells (WBC)	↑ ↓	Creatinine	↑
Hemoglobin	↓	Sodium	↑↓
Platelets counts	↓	Potassium	↑↓
Absolute Neutrophils	↓	Corrected Calcium	↑↓
Absolute Lymphocytes	↑ ↓	Magnesium	↑↓
APTT	↑	Albumin	↓
INR	↑	AST (SGOT)	↑
		ALT (SGPT)	↑
		Total Bilirubin	↑
		Inorganic Phosphate	↓
		Glucose (fasting)	↑↓
		Glucose, plasma (fasting)	↑↓
		Alkaline Phosphatase	↑

↑ Indicates that CTC grade increases as the parameter increases.

↓ Indicates that CTC grade increases as the parameter decreases.

Table 2-5 Laboratory parameters (without CTCAE grades) for which lab reference ranges are defined

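### SAP 2.8.2 withholds CTC grades when the normal range is a placeholder, whereas Protocol 10.5.3.3 requires a missing lower limit to be replaced; the departure is undeclared and may leave some Grade 3-4 low values ungraded

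*Protocol*

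**What the plan says.** Protocol 10.5.3.3 has two rules that bear on a laboratory value without a usable reference range. The first concerns lower limits: "If the lower limits of normal ranges used in CTCAE definitions are missing, then they have to be replaced by a clinical meaningful limit". The second is a default for tests covered by CTCAE: "a Grade 0 will be assigned for all non-missing values not graded as 1 or higher". The protocol's outputs are a table described as "Frequency table for newly occurring on-treatment Grades 3 or 4", shift tables, and a listing of all laboratory data with grades flagged.

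SAP 2.8.2 has a different rule. Its scope is set by the opening words "For the laboratory parameters where the CTC grades depend on the normal ranges". Its trigger is a range entered with the placeholder values 0 and 888888 or higher. Its action is that "the normal ranges and normal ranges indicator should not be present and the corresponding CTC grade should not be derived". No replacement step follows. The imputation rules later in the same section cover values reported as below or above a detection limit, white-cell differentials and corrected calcium, but not missing limits.

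For CTC-graded parameters, the SAP names two outputs: the shift from baseline to worst post-baseline grade, and a "Listing of patients with laboratory abnormalities of CTC grade 3 and 4". SAP section 4, which is reserved for changes to protocol-specified analyses, contains only a COVID-19 subsection.

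**The concern.** For a missing lower limit the two documents point in opposite directions: the protocol keeps the value gradable and the SAP does not. Both CTC outputs named in the SAP need a derived grade. An ungraded value therefore cannot be the worst grade in the shift table and cannot appear in the Grade 3-4 listing. The SAP names no all-data laboratory listing, so the value could be absent from every laboratory output named there. Changes in laboratory parameters are part of the safety endpoint under a secondary objective, so the grading rule should be unambiguous and agree with the protocol.

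**Working it through.** There is no figure in the plan to reproduce. The check sets the rules side by side and traces which grades each one affects.

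**1. Scope of each rule**

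| Situation | Protocol 10.5.3.3 | SAP 2.8.2 |
|---|---|---|
| Lower limit missing | Replace it, then grade | Placeholder range blanked, no grade |
| Upper limit missing | No replacement; Grade 0 default if read literally | Placeholder range blanked, no grade |
| Range simply blank | Lower limit replaced | Not addressed |

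The rules contradict each other in the first row. In the second, neither document supplies a limit.

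**2. Parameters reached by the lower-limit rule.** SAP Table 2-4 has 20 rows, 7 for hematology and coagulation and 13 for biochemistry.
- Rows with a downward grade: WBC, hemoglobin, platelets, neutrophils, lymphocytes (5), plus sodium, potassium, corrected calcium, magnesium, albumin, inorganic phosphate and two glucose rows (8). 5 + 8 = 13.
- Rows graded upward only: APTT, INR, creatinine, AST, ALT, total bilirubin, alkaline phosphatase. 20 - 13 = 7. A lower-limit rule cannot help these.

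**3. Severe grades that need a range.** Protocol Table 6-2 prints some of the thresholds.
- Absolute, no range needed: neutrophils Grade 4 below 500/mm³; platelets Grade 4 below 25,000/mm³; lymphocytes Grade 4 below 0.2 x 10⁹/L. The Grade 3 bands for these three are also absolute.
- Multiples of the ULN: creatinine Grade 4 above 6.0 x ULN; AST/ALT Grade 4 above 20.0 x ULN; bilirubin Grade 4 above 10.0 x ULN. The Grade 3 bands are also ULN multiples.

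**4. Two readings of the SAP rule.** Take a platelet count under 25,000/mm³ reported with a placeholder range.
- Parameter-level reading: platelets is a parameter with a grade that depends on the range, so the value gets no grade. This follows the way the sentence opens.
- Grade-level reading: only the grade that uses the range is withheld, and the value stays Grade 4. The corrected-calcium rule in the same section supports this, because it ties the normal range to Grades 0 and 1 only.

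Under the protocol the value is Grade 4 either way. Two programmers following the SAP could therefore produce different Grade 3-4 listings from the same data.

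**5. Upper-limit grades.** An ALT without a usable ULN cannot be placed in any ULN band. The SAP leaves it ungraded. The protocol's default, read literally, makes it Grade 0, so a markedly raised value could be tabulated as normal. Here the SAP is the safer text, but it leaves the value invisible.

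**6. Size.** Neither document says how many results lack a range, so no count can be derived. As a scale only: 82 patients were randomized to PDR001 (Amendment 06 study status). If all are in the Safety Set, one patient is 1/82 = 1.2 percentage points of a Grade 3-4 rate and two are 2/82 = 2.4. A patient leaves the Grade 3-4 category for a parameter only if no other post-baseline value of that parameter is graded 3 or 4.

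**The case against.** The SAP rule has a sound purpose. If a placeholder of 0 or 888888 were kept, almost any result would fall inside the range and be graded 0. Blanking it is right; the dispute is about what should follow.

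The strongest counter-arguments are these.
- *Ranges should rarely be missing.* A reader might infer that they go missing mainly when a severely ill patient is tested elsewhere, so that the loss is selective. Protocol 7.2.2.5 does foresee this case, "if at any time a patient has laboratory parameters obtained from a different outside laboratory", but the same sentence requires that laboratory's certification and normal ranges to be sent to the sponsor. Protocol 9.4 adds queries for missing values. The documents do not support a claim of non-random loss.
- *The protocol does not replace every limit.* A reader might take the SAP to have discarded liver or renal grades that the protocol would have kept. It has not, because the protocol rule stops at lower limits. An estimate based on ALT would therefore not measure the conflict.
- *Severe low values may survive.* On the grade-level reading they do.
- *Adverse event reporting is a second route.* Protocol 8.1.1 and 8.1.2.1 make a laboratory abnormality an adverse event if it is clinically significant, needs therapy or changes study treatment, and SAP 2.8.1 summarizes those events.
- *Some specifications are not public.* The programming datasets specifications and output shells may settle the matter.

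Most of this stands and limits the point. It does not remove the undeclared contradiction for lower limits or the two possible readings. The adverse event route depends partly on investigator judgement and does not correct the laboratory tables. It is also incomplete: Table 6-2 leaves dosing unchanged for Grade 3 lymphopenia, so a dose change would not trigger reporting there.

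**Conclusion.** The point holds in limited form. For missing lower limits, SAP 2.8.2 departs from Protocol 10.5.3.3 without declaring it. Whether Grade 3-4 neutrophil, platelet and lymphocyte values are lost depends on the reading: they are on the parameter-level reading, while on the narrower one only the range-dependent low grades are. It would go too far to say that severe abnormalities definitely drop out.

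Upper-limit grades without a range are a gap shared by both documents, made worse in the protocol by its Grade 0 default.

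The effect cannot be sized from the documents and may be small, given the requirement to supply ranges. The case for a change rests on the contradiction and the ambiguity, not on an assumed rate of missing ranges. It concerns the final CSR, which is what this SAP covers.

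**What to change.** Amend SAP 2.8.2 as follows.

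1. Derive every CTCAE grade defined by an absolute threshold, whether or not a range is present.
2. Where a grade needs the lower limit and that limit is missing or placeholder-coded, apply the replacement required by Protocol 10.5.3.3 and flag the value. The protocol does not name the replacement limits, so the SAP should state them.
3. Where a grade needs the upper limit and that limit is missing, do not default to Grade 0. List the value as ungraded so that it stays visible. Substituting an upper limit is not proposed, because these limits differ between local laboratories and a borrowed one can misgrade.
4. Record any remaining departure from Protocol 10.5.3.3 in SAP section 4.

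The SAP's introduction already provides for an amendment before database lock or an addendum after it. The cost is a few lines of text, the stated replacement limits, one grading rule and one listing. The downside is that a few grades will rest on a replaced limit, and the flag makes those identifiable.

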#### **10.5.3.4 Other safety data**

Any other safety information collected will be listed and notable values will be flagged. Any statistical tests performed to explore the data will be used only to highlight any interesting comparisons that may warrant further consideration. Additionally, the following outputs will be produced:

##### **ECG (patients in PDR001 arm)**

- Shift table screening/baseline to worst on-treatment result for overall assessments.
- Listing of ECG evaluations for patients treated with PDR001 with at least one abnormality.

##### **Vital signs**

Definitions of notably abnormal results have to be part of the CDP, MAP, CSP and RAP.

- shift table screening/baseline to worst on-treatment result.
- table with descriptive statistics at screening/baseline, one or several post-screening/post/baseline time points and change from screening/baseline to this/these post-screening/post-baseline time points.

#### **10.5.3.5 Supportive analyses for secondary objectives**

Any supportive analyses that are considered appropriate for secondary variables will be described in the RAP prior to database lock.

### 10.5.3.6 Tolerability

Tolerability of study treatment will be assessed by summarizing the number of treatment dose interruptions and dose reductions. Reasons for dose interruptions and dose reductions will be listed by patient and summarized. Cumulative dose, dose intensity and relative dose intensity of PDR001 will be listed by patient and summarized.

### 10.5.4 Pharmacokinetics (patients in PDR001 arm)

The pharmacokinetic parameters that may be assessed are presented in Table 10-1. PK parameters will be determined for all PK-evaluable patients by non-compartmental method(s) using Phoenix (Pharsight, Mountain View, CA). PK parameters listed in Table 10-1 will be calculated and reported, when feasible for PDR001. Concentrations will be summarized by time and in each treatment arm.

**Table 10-1 Noncompartmental pharmacokinetic parameters**

AUClast	The AUC from time zero to the last measurable concentration sampling time (tlast) (mass x time x volume  )
AUCinf	The AUC from time zero to infinity (mass x time x volume  )
AUCtau	The AUC calculated to the end of a dosing interval (tau) at steady-state (amount x time x volume  )
Cmax	The maximum (peak) observed plasma, blood, serum, or other body fluid drug concentration after single dose administration (mass x volume  )
Tmax	The time to reach maximum (peak) plasma, blood, serum, or other body fluid drug concentration after single dose administration (time)
T1/2	The elimination half-life associated with the terminal slope ( $\lambda_z$ ) of a semi logarithmic concentration-time curve (time). Use qualifier for other half-lives
CL	The total body clearance of drug from the plasma (volume x time  )
Vz	The apparent volume of distribution during terminal phase (associated with $\lambda_z$ ) (volume)

PAS will be used in all pharmacokinetic data analysis and PK summary statistics, as appropriate.

#### Pharmacokinetic variables:

The following pharmacokinetic parameters may be determined by profile using non-compartmental method(s) for PDR001:

- AUCinf, AUC0-last, Cmax, Tmax, T1/2, CL and Vz.

Biofluid concentrations will be expressed in mass per volume units. All concentrations below the lower limit of quantitation (LLOQ) or missing data will be reported as such in the concentration data listings. Concentrations below the limit of quantitation will be treated as zero in summary statistics.

[figure not shown]
Descriptive statistics of all pharmacokinetic parameters may include arithmetic and geometric mean, median, SD, and CV, geometric CV, minimum and maximum. Zero concentrations will not be included in the geometric mean calculation. Since Tmax is generally evaluated by a nonparametric method, median values and ranges may be given for this parameter.

Any association/correlation analyses with other endpoints (PK, early clinical activity) will be detailed in the RAP.

### **PD-L1 and potential predictors of efficacy in tumor**

The expression levels of PD-L1, LAG-3 and TIM-3, at screening/baseline will be listed and summarized. The correlation between baseline PD-L1 expression and anti-tumor activity will be explored. Statistical analyses to assess the relationship between biomarker endpoints (PD-L1, LAG-3, TIM-3) and clinical endpoints (e.g. ORR, PFS) will be described in the RAP. All other biomarker data will be listed or summarized as appropriate.

### **10.7 Interim analysis**

No formal interim analyses are planned.

### **10.8 Sample size calculation**

Assuming a 2:1 randomization ratio of PDR001 vs. Comparator, 70 events (PD or death) are to be observed in the randomized Phase II to provide 85% power to detect a 0.55 hazard ratio in terms of PFS (corresponding to a median PFS of 10 months in PDR001 group and 5.5 months in the Comparator group), using a log-rank test at a 1-sided significance level of 0.1.

The final primary analysis of PFS will be done using a Bayesian proportional hazard model when there are at least 70 events observed. Based on the simulation results under different scenarios (see [Appendix 3](#)), 70 events provide reasonable operating characteristics in terms of the probability of obtaining a positive result (as defined in [Section 10.4.2](#)). Using the Bayesian

Cox PH model with mixture MAP prior for the yields reasonable 1-sided type I error (0.081) assuming no efficacy (HR=1) and power (0.92) assuming substantial efficacy (HR=0.55) when current data is in alignment with historical data.

Considering a uniform recruitment time of about 14 months and a 15% drop out rate at 12 months, approximately 114 patients need to be randomized in a 2:1 ratio to the two arms in order to observe 70 events after approximately 6 months follow up (approximately 20 months after FPFV):

- 76 patients to the PDR001 arm
- 38 patients to the control arm

EAST® trial design software v5.4 is used to compute the sample size.

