### 10.4.2 Statistical hypothesis, model, and method of analysis

Patients are randomized in 2:1 ratio into either PDR001 arm or control arm. The primary efficacy endpoint, PFS as determined based on the central tumor assessment per RECIST v1.1, will be analyzed by study arm. Assuming proportional hazards for PFS, the following statistical hypothesis will be tested to address the primary efficacy objective:

$$H_{01}: \theta_1 \geq 1 \text{ vs. } H_{A1}: \theta_1 < 1$$

where  $\theta_1$  is the PFS hazard ratio (PDR001 arm vs control arm). The analysis to test this hypothesis will consist of a stratified log-rank test at an overall one-sided 10% level of significance. The stratification factor is disease status (locally advanced recurrent NPC vs. metastatic NPC).

As a supportive analysis, a Bayesian Cox proportional hazard (PH) model (see [Appendix 3](#)) will be used to estimate the hazard ratio for PFS between the two treatment combination arms. The final analysis will be performed when 70 events (progressive disease or death due to any cause) are observed from the study.

An evidence-based prior for the non-parametric, interval-specific hazards of the control arm in the Bayesian Cox PH model is derived using available historical PFS data from the list of the phase II studies (see [Table 1-1](#) and [Appendix 3](#)), using the meta-analytic-predictive (MAP) approach ([Neuenschwander et al 2010](#)) with the assumption of moderate/large between-trial heterogeneity. For more details about the model specification including the prior derivation and its operating characteristics please refer to [Appendix 3](#).

Based on the historical studies, the median PFS for the patients in the control arm is assumed to be 5.5 months (165 days).

The dual-criterion for success based on Bayesian Cox PH model is defined to show a positive result if there is enough evidence that monotherapy PDR001 is superior to the control with respect to the primary PFS endpoint, such that:

- Posterior probability ( $HR > 1$ )  $< 10\%$ , and
- Posterior median  $HR < 0.7$

The posterior median of the HRs along with the associated 95% two-sided credible intervals will be produced for the treatment comparison of PDR001 to the control. In addition, the posterior probability that the true HR lies in the following intervals will be produced:

- Substantial efficacy:  $[0, 0.55)$
- Moderate efficacy:  $[0.55, 0.7)$
- Slight efficacy:  $[0.7, 1)$
- No efficacy:  $[1, \infty)$

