#### 14.3.1.1 Model specification

The primary analysis of progression free survival (PFS) will be based on a Bayesian Cox PH model. This model will be used to estimate the hazard ratio for PFS of PDR001 vs. SOC. This model assumes that the hazard function of individual in treatment group  $i$  (PDR001 or SOC) can be expressed as;

$$\lambda_i(t) = \lambda_0(t)e^{\beta X_i}$$

Here  $\lambda_0(t)$  is the baseline hazard (or hazard for SOC),  $X_i$  indicates the treatment group membership (0 for SOC and 1 for PDR001) and  $\beta$  denotes the log hazard ratio (HR) between PDR001 group and the SOC group. Furthermore baseline or SOC group hazard function  $\lambda_0(t)$  is modeled via a piece-wise exponential model. This is a semi-parametric model which subdivides time into reasonably small  $K$  intervals and assumes that the baseline hazard is constant in each interval. i.e.,

$$\text{for } \lambda_0(t) = \lambda_{ck} \quad t \in (I_{k-1}, I_k] \quad k = 1, 2, \dots, K$$

Note that the  $\lambda_{ck}$  refer to hazard for unit time (per day). Sampling model (or likelihood) under this framework can be constructed using Binomial distribution. In this model for each of the  $K$  time intervals, the number of events in the SOC group ( $r_{ck}$ ) and PDR001 group ( $r_{Tk}$ ) follow Binomial distributions with interval-specific hazards  $\lambda_{ck}$ . Under the proportional hazards assumption it follows that

---

SOC data:	$r_{ck} \sim \text{Binomial}(n_{ck}, 1 - e^{-\lambda_{ck}L_k}),$
-----------	--

---

PDR001 data:	$r_{Tk} \sim \text{Binomial}(n_{Tk}, 1 - e^{-\lambda_{ck}e^{\beta}L_k})$
--------------	--

---

where  $n_{ck}$  and  $n_{Tk}$  are risk sets for event in the SOC and PDR001 groups, respectively, in interval  $(I_{k-1}, I_k]$  and  $L_k$  is the length of the  $k$ -th interval.

The study plans to enroll approximately 114 patients to accrue 70 events for the primary analysis of PFS endpoint. This study will be considered successful if there is sufficient evidence that the monotherapy of PDR001 is superior to SOC in PFS based on the evaluation criteria, i.e.:

- Posterior probability (HR>1) < 10%, and
- Posterior mean HR<0.7.

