#### 14.3.2.2 Simulation study description

Each of the above described scenarios is investigated based on simulated data over 1000 trials. The following assumptions are made in order to run these simulations:

1. The time to event (PD or death), censoring time and accrual time are all assumed to follow exponential distribution. For all the above scenarios the accrual is assumed to be 8 patients per month.
2. The End of Study is assumed to be at the day of 70th event.

Simulation is performed in the following steps:

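### The protocol names two primary analyses of PFS, a stratified log-rank test and a Bayesian Cox model, and their success rules can disagree

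*Protocol*

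**What the plan says.** Three places in the current protocol assign the primary role, and they do not agree.

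- **Section 10.4.2** states the hypothesis on the PFS hazard ratio. The analysis to test it "will consist of a stratified log-rank test at an overall one-sided 10% level of significance". The next paragraph begins "As a supportive analysis, a Bayesian Cox proportional hazard (PH) model". Further down, the same section says: "The dual-criterion for success based on Bayesian Cox PH model is defined to show a positive result". That rule requires a posterior probability below 10% that the hazard ratio exceeds 1, and a posterior median hazard ratio below 0.7.
- **Section 10.8** sizes the trial on a log-rank test at one-sided 0.1, then says: "The final primary analysis of PFS will be done using a Bayesian proportional hazard model when there are at least 70 events observed". It supports the 70 events with the Bayesian type I error (0.081) and power (0.92).
- **Section 14.3.1.1 (Appendix 3)** says: "The primary analysis of progression free survival (PFS) will be based on a Bayesian Cox PH model". It goes on: "This study will be considered successful if there is sufficient evidence that the monotherapy of PDR001 is superior to SOC in PFS". Its criteria are the same 10% posterior probability and "Posterior mean HR<0.7", a mean where 10.4.2 and Step 4 of the simulation use the median.

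Step 5 of the simulation (14.3.2.2) says positive rates were calculated for both approaches. Table 14-10 has a single type I error/power column, whose values are those that 10.8 and 14.3.2.3 attribute to the Bayesian model. SAP 2.2.3 reports that the primary efficacy analysis in the interim CSR did not reach statistical significance, without naming the test.

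**The concern.** The primary analysis and its success rule should be readable in one way only. Here a reader of 10.4.2 would declare success on the log-rank p-value, and a reader of 14.3.1.1 on the Bayesian dual criterion. The two can give opposite answers on the same data. The Bayesian rule borrows historical control information, so its error rate moves with the control arm's PFS.

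Timing adds to the need for clarity. The Amendment 04 change list records the addition of the log-rank test to 10.4.2. That amendment is dated 7 December 2017, and its study status gives 114 patients already randomised at 16 October 2017. The trial is open-label, and section 8.5 has the study team monitoring the primary endpoint quarterly. At stake is what the reported result can be taken to show.

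**Working it through.** **Inputs.** From 10.8: 70 events, 2:1 allocation, one-sided alpha 0.10, hazard ratio (HR) 0.55, 85% power, 114 patients, 15% drop-out at 12 months. From Tables 14-9 and 14-10: control medians, true HRs and Bayesian positive rates. From 14.3.2.2: exponential times, 1000 simulated trials, analysis at the 70th event, and "For all the above scenarios the accrual is assumed to be 8 patients per month".

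**1. The plan's own figure (Schoenfeld).** Events needed = (1.2816 + 1.0364)² / [(2/9) × (ln 0.55)²] = 67.7, so 68 against the stated 70. SE(log HR) at 70 events = 1/√(70 × 2/9) = 0.2535. Power at HR 0.55 = Φ(0.5978/0.2535 − 1.2816) = 0.859; at HR 0.67 it is 0.617. The stated sizing reproduces, and it belongs to the log-rank test.

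**2. Log-rank threshold.** Critical observed HR = exp(−1.2816 × 0.2535) = 0.723.

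**3. The two rules compared.** The log-rank test was simulated, unstratified, on the inputs above. Drop-out of 15% at 12 months is an assumption here, because Appendix 3 gives no censoring rate. The first log-rank figure comes from 20,000 trials per scenario and the second from a separate run of 8,000.

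| Scenario | Control median (months), HR | Log-rank positive | Bayesian positive (Table 14-10) | Bayesian minus log-rank |
|---|---|---|---|---|
| 1 | 5.5, 1 | 0.108 / 0.105 | 0.081 | −0.027 / −0.024 |
| 2 | 5.5, 0.55 | 0.871 / 0.877 | 0.922 | 0.051 / 0.045 |
| 3 | 5.5, 0.67 | 0.636 / 0.645 | 0.727 | 0.091 / 0.082 |
| 4 | 7.5, 1 | 0.104 / 0.104 | 0.191 | 0.087 / 0.087 |

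With no drop-out the log-rank rates are 0.108, 0.874, 0.629 and 0.107, so the assumption matters little for the log-rank side. Scenario 6 is left out because its medians give 7.5/12.9 = 0.58, not the stated 0.67.

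**4. From rates to disagreement.** P(Bayesian positive and log-rank negative) ≥ P(Bayesian positive) − P(log-rank positive). A positive difference in the table is therefore a lower bound on the share of trials positive on the Bayesian rule only. A negative one bounds the reverse.

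**5. Monte Carlo error in Table 14-10.** Exact 95% limits for 1000 trials are 0.167–0.217 (scenario 4), 0.698–0.754 (scenario 3), 0.904–0.938 (scenario 2) and 0.065–0.100 (scenario 1). Using the lower limits with the 20,000-trial rates, the bounds become 0.063, 0.062 and 0.033 for scenarios 4, 3 and 2. In scenario 1 the log-rank rate lies above the whole Bayesian interval; the bound falls from 0.027 to 0.008.

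**6. What these limits do not cover.** A re-implementation of the Bayesian rule (600 trials) gave 0.130 or 0.170 in scenario 1, depending on how the mixture prior is read, against the printed 0.081. Table 14-10 could not be reproduced, so its rates are used as printed.

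**7. Mean versus median.** As an approximation with a vague control prior (an assumption, not the planned prior), the posterior mean is the median × exp(0.2535²/2). A mean below 0.7 then needs a median below 0.678. Type I error moves from about 0.080 to 0.063, and power at HR 0.55 from about 0.829 to 0.795.

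**The case against.** The strongest reply is that the intent is plain. Table 3-1 sends the reader to 10.4, where only the log-rank test carries the hypothesis and the alpha; the sizing uses it; and a report phrased as statistical significance fits a frequentist test. The Amendment 04 list has an entry for 10.4.2 but none for 10.8 or Appendix 3, so those are probably text that was not updated. A supportive model may also have its own criterion for a positive finding, so that part of 10.4.2 is not by itself a contradiction. All of this stands as an account of how the conflict arose. It does not remove it: two current sections still call the Bayesian model primary, and one makes it the test of study success.

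It can also be said that enrolment is closed and the primary result is out. That limits the remedy to wording and disclosure.

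Some stronger inferences are tempting and should not be drawn.

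- **That the log-rank test was brought in because of accumulating data.** The documents show when it entered 10.4.2, not why, nor what 10.4.2 said before.
- **That the trial's type I error is 0.191.** That holds only if the Bayesian rule is primary and controls have a 7.5-month median.
- **That the two rules disagreed on the actual data.** Nothing provided shows this.
- **That the SAP is at fault for naming no test in 2.6.2.** It covers the final CSR, while the primary analysis was reported in an interim CSR whose plan is not among the documents.
- **That the predictive probability of success in section 8.6 rests on an undefined rule.** It appears there only as an example of data that might be sent if a continuation decision arose.

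**Conclusion.** The contradiction is real and concerns the main decision rule. Read as log-rank, the trial has nominal type I error 0.10 and power of about 0.86 to 0.88 at HR 0.55. Read as Bayesian, Table 14-10 gives type I error 0.081 or 0.191, and power 0.922 at HR 0.55 with 5.5-month controls.

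On that table as printed, with the assumed drop-out, trials positive on the Bayesian rule only make up at least about 9% of null trials with 7.5-month controls. With 5.5-month controls the figures are at least 8–9% at HR 0.67 and 4–5% at HR 0.55. In the aligned null scenario the disagreement runs the other way, at about 2–3%. The limits in step 5 allow for Monte Carlo error in the printed rates only, not for an error in the table.

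Importance lies between should-fix and must-fix: patients, events and data are unaffected, but what the trial can conclude is not.

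**What to change.** 1. Reconcile 10.4.2, 10.8 and 14.3.1.1 to one primary test and one success criterion. The stratified log-rank test at one-sided 0.10 is the natural choice, because it carries the hypothesis, the alpha and the sizing, provided it is the test pre-specified for the interim CSR. Label the Bayesian model and its dual criterion supportive throughout, and do not cite its 0.92 power for the primary test.
2. Relabelling after the result is known is not enough. State in the SAP or CSR which test gave the non-significant result and that the log-rank test entered 10.4.2 at Amendment 04, after 114 patients had been randomised. Report the outcome of the other rule beside it.
3. Align the posterior mean in 14.3.1.1 with the posterior median, after checking which one the simulation code used.
4. Add to Table 14-10 the frequentist positive rates that Step 5 says were calculated.

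The cost is wording in three protocol sections, one table column from simulation output that should already exist, one code check and a short statement in the SAP or CSR. The sponsor gives up the more favourable power figure, and any disagreement between the two rules on the reported data becomes visible.
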